2.0 STUDY OBJECTIVES AND DESIGN

2.1 Primary Objective

To determine whether the peer-educator intervention reduces the rate of HIV infection among injection drug users and members of their HIV risk network

2.2 Secondary Objectives

- 1. To determine whether the intervention reduces reported injection and sexual HIV risk behaviors in index participants and/or network members
- 2. To determine whether the intervention changes substance use network norms for injection and sexual HIV risk practices
- 3. To determine whether the intervention effects on injection and sexual HIV risk behaviors differ between index and network participants, or by HIV status in each study arm
- 4. To determine whether the intervention effect on behaviors identified as important mediators of the intervention is similar at both sites

2.3 Study Design

This is a Phase III, multi-site, two-arm, randomized, controlled study of a network-oriented peer education training intervention for the prevention of HIV infection through reduction of HIV risk behaviors among HIV-uninfected IDUs and members of their HIV risk networks. (See study design and randomization schema on page 3.)

IDUs will be recruited using street and community outreach methods in Chiang Mai and Chiang Rai, Thailand, and Philadelphia, Pennsylvania, USA. Outreach workers will supply basic

information about the study in geographic areas and settings frequented by drug users and will encourage these individuals to seek screening at a local study site. Individuals who present at the study clinic will undergo informed consent for screening, a screening eligibility survey, and HIV counseling and testing. Individuals will be told when to return for their HIV test results, post-test counseling and further screening. Those who are HIV-uninfected, who meet preliminary eligibility requirements, and are willing to participate, will undergo informed consent for the study. These persons are referred to as **index participants** throughout the protocol. Each index participant will then be asked to identify and attempt to recruit at least two members of his/her sex and/or drug HIV risk network. One or more of the network members identified must complete all screening procedures and be determined eligible for this network to be randomized and enrolled. These HIV risk network members are referred to as network members throughout the protocol. HIV-infected and uninfected network members are eligible for enrollment. HIVinfected network members will not contribute to the primary efficacy analysis, although they will contribute to secondary endpoint analyses. Inclusion of HIV-infected network members will ensure that the networks enrolled broadly represent the IDU populations at the study sites. It will also help preserve the confidentiality of the HIV status of each participant. These network members will be offered referrals to support services as described in Section 8.4.1. Adjustments will be made to the study sample size in the event that the number of HIV-infected network members enrolled could substantially reduce the study's ability to detect an intervention effect. See Section 3.4 for details on the recruitment process.

The two sites proposed for this study have substantially different baseline rates of seroincidence. Traditionally, the rationale for combining data from different settings is to achieve both sufficient power and generalizability. With respect to power, the current design attains most of its strength from the higher seroprevalence site. However, the results of a single site protocol cannot be convincingly generalized, particularly for behavioral interventions where cultural setting is arguably a significant modifier of effect. If the intervention is implemented in Thailand and Philadelphia and the overall relative risk after adjusting for site is statistically significant, then the analysis of behavioral mediators of the intervention effect can provide a scientific basis for claiming the intervention is effective in different settings. For this reason, the intervention will be implemented in these two sites.

Index participants will be randomized in a 1:1 ratio with their network members to one of two study arms. Index participants and network members in both study arms will receive enhanced HIV counseling aimed at risk reduction in conjunction with HIV testing (see Section 4.2). In addition, index participants randomized to the experimental arm will receive six two-hour peer educator-training sessions in groups of up to 12 over a period of four weeks. The training sessions will focus on skills building with respect to risk-reducing behaviors and the promotion of such behaviors to network members (see Section 4.1). There also will be a one to two hour booster training session held for the index participants after their six and 12-month follow-up assessments. Network members in the experimental arm are expected to receive indirect benefits through their interactions with their index participants. Average network HIV incidence rates will be compared across the two arms of the study.

All participants will be administered a risk behavior survey at screening prior to provision of risk reduction counseling to measure baseline risk behavior and a questionnaire to assess perceived network norms. In addition, to assess the network characteristics and intensity of intervention delivery by the index, both indexes and network members will be administered questionnaires about the frequency and duration of contact and types of discussions between them.

Index participants and network members will have follow-up visits every six months. The study duration will be approximately 48 months. Enrollment is expected to take approximately 30 months. Participants will be followed for a minimum of 18 months and a maximum of 30 months at each site. Every six months, participants will be administered surveys designed to assess the following: HIV risk behavior; network characteristics; the intensity of the intervention delivery; social harms experienced that may be associated with study participation; and intervention contamination in the control arm (i.e. sources of exposure to HIV prevention-related messages and materials). In addition, perceived network norms will be assessed annually. The behavioral risk survey will be administered prior to risk reduction counseling by an individual other than the person who administered the counseling. Behavioral risk survey interviewers will be blinded to the study arm of the participants.

To enhance retention, participants will be contacted in-between their scheduled six-month followup visits to update their locator information (e.g., address, telephone number, name and address of family members), confirm or re-schedule their next follow-up visit and reinforce instructions to contact the study site to update locator information. Also, any difficulties experienced in contacting participants at these time points will serve to trigger timely mobilization of outreach efforts to ensure that participants are located in time for their next scheduled follow-up visit. The contacts may be conducted in-person at the study site, via telephone, or via street/home outreach.

3.0 STUDY POPULATION

HIV-uninfected IDUs (index participants) and members of their HIV risk network (network members), irrespective of their HIV status, will be included in this study. Participants will be enrolled in the study according to the criteria in Sections 3.1 and 3.2. They will be recruited as described in Section 3.3 and 3.4 and assigned to a study intervention arm as described in Section 7.4. Conditions for withdrawal from the study are described in Section 3.7.

3.1 Inclusion Criteria

3.1.1 Index Participants

Individuals must meet all of the following criteria to be eligible for inclusion in the study as an **index participant:**

- Of legal age to independently provide written informed consent for research
- Provide written informed consent for screening and study participation
- Report having injected drugs at least 12 times in the last three months
- Been out of methadone maintenance treatment for at least 3 months and have relapsed
- HIV negative on specimen obtained within 60 days prior to randomization
- Willing to identify and attempt to recruit at least two HIV risk network members who are eligible for study participation according to the criteria in Sections 3.1.2 and 3.2.2.
- Able to recruit at least one HIV risk network member who is eligible for study participation according to the criteria in Sections 3.1.2 and 3.2.2.

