3.5 Enrollment of Networks and Randomization

Prospective index participants in networks consisting of one or more eligible network members (either HIV-negative or positive) will be contacted within 60 days of their HIV pre-test counseling visit to learn of their eligibility status. All individuals to be randomized must have initiated screening procedures fewer than 60 days prior to the planned date of randomization. Individuals who exceed this 60-day limit may be re-screened, and all screening procedures must then be completed before their network is qualified for randomization. Index participants will be randomized along with their network member(s) to either the experimental or control arm. Study staff will contact index participants and network members to confirm their enrollment status.

If no prospective network members identified by an index have presented for screening, been found to be eligible, and provided study consent within the 60 days following the index participant's pre-test counseling visit, the index participant will be considered ineligible for the study as a member of that network.

Note: Individuals who initially screen (and provide consent) as an index member may subsequently be screened as a network member for another network, but must first complete the network member informed consent process and member screening assessment. As above, if the time between the participants initial HIV blood draw and enrollment/randomization of the network exceed 60 days, screening procedures as specified in the SSP manual must be repeated.

Note: Individuals who initially screen as a network member may subsequently be screened as a network member for another network, but must first complete the member screening assessment for each network they are screening for. As above, if the time between the participants' initial HIV blood draw and enrollment/randomization of the network for which they qualify exceed 60 days, screening procedures as specified in the SSP manual must be repeated.

Note: Individuals who initially screen as a network member may not screen as an index member for 3 months after their initial blood draw for HIV testing to allow for the dissipation of any

measurement effects. After this three-month period, the individual may undergo the screening procedures as an index member after completing the index screening informed consent process.

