5.3 Follow-up Visits

Follow-up visits are scheduled to take place every six months from enrollment/randomization until the study end date; however, they may take place any time within the period extending from 14 days prior to the target date to 30 days after the target date. Visits that do not take place during this period are treated as interim visits (see Section 5.5). Post-test counseling visits will occur either the same day (for rapid tests) or in approximately 7 to 14 days (for non-rapid tests) after HIV testing. For the purposes of scheduling follow-up visits, a single "Day 0" enrollment/randomization will be assigned to all network members according to the randomization date of their respective index.

Participants will undergo the following:

- Identity confirmation
- Update locator information
- Risk Behavior Survey Note: The risk survey must be administered prior to the delivery of HIV counseling, by a staff member who has not previously provided HIV counseling to the participant and is blinded to participant' study arm assignment.
- Enhanced risk reduction counseling
- HIV testing according to Appendix I
- Follow-up questionnaire to assess the intensity of the intervention delivery by the index in indexes themselves and network members (duration of contact and types of discussions), intervention contamination in the control arm, and perceived network norms (every 12 months)
- Social harms assessment
- Reiteration of study site contact information and instructions to contact the site for additional information about the study and/or HIV counseling, if needed, prior to the follow-up HIV post-test counseling visit.

Note: Network members identified as HIV-infected at baseline and index participants and network members identified as HIV-infected after enrollment will remain in follow-up and undergo all scheduled assessments except HIV testing.

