7.3.1 Power for seroincidence endpoints

Philadelphia has established a seroincidence rate of 2 per 100 person-years and the current rate established in Thailand among IDU is 10.4 per 100 person-years, although in the sample size computations a conservative 8% rate is used. One-third of the networks will enroll in Philadelphia and two-thirds in Thailand.

Sample size computations are made using the following assumptions:

- Mean seroincidence rate: 6% per year for pooled sites, 8% per year for the Thai sites.
- Loss to follow up 10% per year
- 30 months recruitment, minimum 18 months follow up, maximum 30 months
- 90% power, 5% Type I error

The formula above is used, substituting for P_E and P_C estimates \overline{P}_E and \overline{P}_C , the average probability of seroconverting during the study on the experimental and control arms. These estimates take loss to follow-up and differential length of follow-up into account.

Rate	Effect	\overline{P}_{F}	\overline{P}_{c}	K	Total/	Networks/	Total/	Networks/	Total/	Networks/
		L	C		arm	arm	arm	arm	arm	arm
					Mean pe	er network $= 4$	Mean pe	er network $= 3$	Mean pe	er network $= 2.5$
6%	33%	7.8%	11.6%	0.1	1671	418	1542	515	1478	592
				0.2	2057	515	1800	600	1671	669
				0.3	2442	611	2057	686	1864	746
6%	40%	7.1%	11.6%	0.1	1112	278	1026	343	983	394
				0.2	1368	343	1197	400	1112	445
				0.3	1625	407	1368	457	1240	496
8%	33%	10.4%	15.3%	0.1	1246	312	1150	384	1102	441
				0.2	1534	384	1342	448	1246	499
				0.3	1821	456	1534	512	1390	556
8%	40%	9.4%	15.3%	0.1	828	208	765	255	733	294
				0.2	1020	255	892	298	828	332
				0.3	1211	303	1020	340	924	370

 Table 1: Sample size requirements for two-arm group randomized network study

The sample size has been chosen to achieve 90% power to detect a 40% reduction in rate of infection, from 6% per year to 3.6% per year. This requires 445 networks per arm, followed for an average of 27 months (minimum of 18 month, maximum of 30 months), with a seroincidence evaluation of an average of 2.5 HIV-uninfected people per network (HIV-uninfected peer leader and one or more network members, HIV-uninfected at enrollment) and loss to follow-up of 10% per year, using two-sided alpha of 0.05 and intraclass correlation of 0.2. To achieve the same power to detect a 33% reduction, from 6% to 4%, requires 669 networks per arm.

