9.0 LABORATORY SPECIMENS AND BIOHAZARD CONTAINMENT

9.1 Local Laboratory Specimens

Eight mL of blood will be collected from each participant for HIV testing and stored at the local laboratory at screening and every six months thereafter.

Each study site will adhere to standards of Good Laboratory Practice, the HPTN Manual of Operations, and local standard operating procedures for proper collection, processing, labeling, transport, and storage of specimens to the Local Lab (LL). Specimen collection, testing, and storage at the LL will be documented using the HPTN Laboratory Data Management System (LDMS).

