9.2 Laboratory Quality Assurance

The HPTN CL has established a proficiency testing program at each study site. CL staff also will conduct periodic visits to each site to assess the implementation of on-site laboratory quality control procedures, including proper maintenance of laboratory testing equipment, use of appropriate reagents, etc. CL staff will follow-up directly with site staff to resolve any quality control or quality assurance problems identified through proficiency testing and/or on-site assessments.

The HPTN CL will repeat HIV antibody testing on all specimens from HIV seroconverters and a random sample of stored specimens for quality assurance (QA) purposes. The CL will inform site staff of the samples selected for quality assurance testing, and site staff will ship the selected specimens to the CL. All specimens will be shipped in accordance with the HPTN Manual of Laboratory Operations and IATA specimen shipping regulations. All shipments will be documented using the HPTN LDMS

The CL will test the specimens for HIV antibody and compare the results of their tests with the results obtained by the local labs. CL staff will follow up directly with site staff to resolve any quality assurance problems identified through this process.

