9.3 Specimen Storage

Study site staff will store all plasma specimens for enrolled participants collected in this study at least through the end of the study. All plasma specimens for enrolled participants will be subject to possible quality assurance testing — for HIV antibody — as described in Section 9.2. Specimens from non-enrolled participants may be discarded one year following the collection date.

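### HIV status is fixed by an antibody test up to 60 days before Day 0 and never rechecked for early infection, so some infections that precede randomisation count as endpoints and slightly dilute the effect

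*Protocol*

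**What the plan says.** - Protocol Section 3.1.1 requires of the index: "HIV negative on specimen obtained within 60 days prior to randomization". Section 3.5 sets the same limit for everyone: "All individuals to be randomized must have initiated screening procedures fewer than 60 days prior to the planned date of randomization". Section 5.1.2 counts the 60 days from the pre-test visit of whoever in the network was screened first.
- Section 9.1 provides for blood for "HIV testing and stored at the local laboratory at screening and every six months thereafter". The visit procedures table marks HIV testing at screening and from month 6, with nothing at Day 0. Section 5.3 fixes the origin of follow-up: "Follow-up visits are scheduled to take place every six months from enrollment/randomization".
- On retesting, Section 9.2 states: "The HPTN CL will repeat HIV antibody testing on all specimens from HIV seroconverters". Section 9.3 adds: "All plasma specimens for enrolled participants will be subject to possible quality assurance testing — for HIV antibody".
- Section 7.2.1 defines the primary endpoint through the seroconversion algorithm of Appendix I, which is titled as an antibody algorithm.
- Section 7.3.1 describes the people evaluated for seroincidence as "HIV-uninfected peer leader and one or more network members, HIV-uninfected at enrollment". It also excludes HIV-infected network members from the primary analysis.

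**The concern.** The procedures establish that a participant was antibody-negative at the screening draw. They do not establish that the participant was uninfected at enrollment. Two groups can be infected before randomisation and still be scored as incident cases: those infected but not yet antibody-positive at the draw, and those infected between the draw and Day 0. An antibody retest of the stored screening sample would again read the first group as negative. For the second group there is no specimen at all.

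The intervention could not have prevented these infections. They occur at the same rate in both arms, pull the hazard ratio toward 1 and cost some power. The index is normally tested first and then waits while members are recruited and screened, so the gap tends to be longest for the people who are trained. The attenuation allowance in Section 7.3.4 covers contamination between arms only.

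**Working it through.** **Inputs from the protocol (Section 7.3.1):** control seroincidence 6% per year; P_E = 0.071 and P_C = 0.116; kappa = 0.2; n = 2.5 uninfected people per network; 1,112 participants (445 networks) per arm; two-sided alpha 0.05; power 90%. About 2,250 uninfected participants are planned in total, with 900 indexes and 1,350 members.

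**Assumptions (not in the protocol):** mean gap from draw to Day 0 of 30 days; antibody-negative period of 25 days (range 14–42).

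**1. Reproduce the plan.** T = (z_α + z_β)² [P_E(1−P_E) + P_C(1−P_C)] [1 + (n−1)κ] / (P_E−P_C)² = (1.960 + 1.282)² × 0.1685 × 1.3 / 0.045² ≈ 1,137 per arm, or 455 networks. The protocol prints 1,112 and 445, about 2% lower, which fits rounding of the printed probabilities. Solved for power at T = 1,112, the formula gives 89.4%. The planned risk ratio is 0.071/0.116 = 0.612, and planned events are 1,125 × (0.071 + 0.116) ≈ 210.

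**2. Add infections that precede Day 0.** Risk per person a = 0.06 × (gap + window)/365, the same in both arms, is added to P_E and P_C. Extra events are 2,250 × a.

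| Gap (days) | Window (days) | Extra events | Share of counted events | Risk ratio | Power |
|---|---|---|---|---|---|
| 0 | 0 | 0 | 0% | 0.612 | 89.4% |
| 30 | 0 | 11.1 | 5.0% | 0.628 | 88.0% |
| 30 | 14 | 16.3 | 7.2% | 0.635 | 87.3% |
| 30 | 25 | 20.3 | 8.8% | 0.640 | 86.8% |
| 30 | 42 | 26.6 | 11.2% | 0.648 | 86.0% |
| 42 | 25 | 24.8 | 10.5% | 0.646 | 86.2% |

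Central case: a = 0.06 × 55/365 = 0.0090. If a person infected before Day 0 is removed from later risk, using a + (1−a)P, power is 86.4% instead of 86.8%.

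The last row puts every index at 60 days and every member at 30 (assumption): (900 × 60 + 1,350 × 30)/2,250 = 42 days.

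**3. What a test of the screening plasma can remove.** Only infections present at the draw: 2,250 × 0.06 × 25/365 = 9.2 (5.2 at 14 days, 15.5 at 42 days). With a 30-day gap, power returns from 86.8% to 88.0%. The gain is 1.2 points, ranging from 0.7 (87.3% to 88.0%) to 2.0 (86.0% to 88.0%).

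**4. Concentration at month 6.** True infections in the first half-year, ignoring loss: control 1,125 × 0.06 × 0.5 = 33.8; experimental 1,125 × 0.036 × 0.5 = 20.3; together 54. Adding 20.3 earlier infections makes them 20.3/74.3 = 27% of first-visit events. The apparent ratio there is (20.3 + 10.2)/(33.8 + 10.2) = 0.69, against a true 0.60.

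**5. Assay count.** At most 54 + 20 ≈ 74. With a 25-day detection delay the 54 falls to 54 × (182.5 − 25)/182.5 ≈ 47, giving about 67. Hence roughly 65–75.

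**The case against.** The strongest case against is about size.

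- **Validity is not threatened.** Infections before randomisation are balanced by allocation. A reader might infer that a positive result becomes suspect. It does not: the error is conservative and type I error is unaffected. This stands.
- **The 60-day figure is a ceiling.** A reader might put all 2,250 people at 60 days plus 25, giving about 31 events, a risk ratio of 0.65 and power of 85%. The protocol does not allow that pattern: the clock in Section 5.1.2 starts with the first person screened, and members are normally screened after the index (Sections 3.4 and 5.1). This stands, and the upper scenario above is set accordingly.
- **The fix is partial.** A reader might assume that the whole 2.6-point loss is recoverable. Less than half of it is.
- **Incidence is not overstated by the full count.** The antibody-negative period also hides infections acquired just before the last test. At the average planned rate of 4.8% and about 80% still followed (assumption), 2,250 × 0.048 × 25/365 × 0.8 ≈ 6 are missed, against 9 added. This offsets the incidence estimate but does not undo the dilution of the ratio.
- **There may be planning reserve.** Section 7.3.1 cites 10.4 per 100 person-years in Thailand but plans on 8%. With 10.4 and 2 in a 2:1 mix the pooled rate is 7.6%, and scaling P_E and P_C by 7.6/6 gives power of about 96%. However, Section 3.3 reports 7.89 for the Thai cohort, so the reserve is not secure, and it would not correct the diluted estimate.
- **Some material is not visible.** The Appendix I flow charts are not shown, and an analysis plan could set a rule for first-interval seroconversions. It could not create an RNA or antigen result that the laboratory section does not provide for.
- **The 60 days are a deliberate allowance** for forming networks. That is reasonable, and this point does not ask to shorten them.

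**Conclusion.** The point holds as a minor one. Section 7.3.1 claims a status at enrollment that the testing schedule does not establish, and some infections that precede randomisation will be counted as endpoints. In the central case this is about 20 events, 9% of those counted and about a quarter of those at month 6. The risk ratio moves from 0.61 to 0.64 and power from 89.4% to 86.8%. With a mean gap of 42 days power is about 86%. Because the affected events cluster at the first visit, early looks by the monitoring board would see more dilution than the whole-study average.

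The figures rest on assumed values for the mean gap and the antibody-negative period, and on the protocol's cumulative-risk formula, whereas the planned analysis is a Cox model.

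**What to change.** 1. In Sections 9.2 and 9.3 and Appendix I: for each participant first antibody-positive at the first follow-up test, have the central laboratory test the stored screening plasma for HIV RNA or p24 antigen without knowledge of arm. Classify positives as infected at baseline and exclude them from the primary endpoint, in line with the existing exclusion of HIV-infected network members.
2. In Section 7.3.1: describe the analysed participants as HIV antibody-negative at the screening draw, up to 60 days before randomisation, in place of the present description.
3. Acknowledge infections acquired between the draw and Day 0 as residual dilution that this testing cannot remove.

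**Cost:** about 65–75 assays on plasma that Section 9.3 already keeps to the end of the study and Section 9.2 already has retested; consent wording to cover the added assay; and about 5–16 fewer endpoints. **Gain:** about one point of power (0.7 to 2.0) and an accurate description of the population.
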